5. PATIENT SELECTION

5.1. Inclusion Criteria

1. Hospitalization for confirmed PCR positive COVID-19 infection
2. Active cancer, defined as a solid malignancy either undergoing active therapy, receiving therapy within 1 year, or a hematologic malignancy under active therapy or observation.
3. Age ≥ 18
4. Patients with evidence of pulmonary involvement who meet any of the followings; presence of infiltrates on chest X-ray or CT scan or need for supplemental oxygen $< 8\text{L}$ nasal cannula or pulse oximetry $< 94\%$ on room air.
5. Biochemical values within the following limits:
 - a. Creatinine clearance $\geq 25 \text{ ml/min}$ by Cockcroft-Gault equation

- b. Total bilirubin $\leq 1.5 \times$ upper limit of normal (ULN) unless bilirubin rise is due to Gilbert's syndrome or of non-hepatic origin
- c. Alanine aminotransferase (ALT) and aspartate aminotransferase (AST) $\leq 3 \times$ ULN
- 6. Hematology values must be within the following limits (no need to hold growth factors or transfusions):
 - a. Absolute neutrophil count (ANC) $\geq 1000/\text{mm}^3$ independent of growth factor support
 - b. Platelets $\geq 50,000/\text{mm}^3$
- 7. Ability to swallow capsules or receive opened capsule content via nasogastric or enteral feeding tube as described in 7.2
- 8. Ability to provide informed consent indicating that they understand the purpose of and procedures required for the study, including biomarkers, and are willing to participate in the study. If a patient is unable to provide informed consent (e.g. does not possess decisional capacity), a legally authorized representative may provide consent for the patient.
- 9. Women of childbearing potential and men who are sexually active must be practicing a highly effective method of birth control during and after the study consistent with local regulations regarding the use of birth control methods for subjects participating in clinical trials. Men must agree to not donate sperm during and after the study. For females, these restrictions apply for 1 month after the last dose of study drug. For males, these restrictions apply for 3 months after the last dose of study drug.
- 10. Women of childbearing potential must have a negative serum (beta-human chorionic gonadotropin [β -hCG]) or urine pregnancy test at Screening. Women who are pregnant or breastfeeding are ineligible for this study.

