Enrollment to this dose level will stop if 2 of the first 3 evaluable patients or if at least 33% of subsequent evaluable patients (i.e, 2/6, 3/9, or 4/12) have DLT. If unacceptable toxicity is observed, Ibrutinib will decrease to 280 mg daily, and another 12 patient lead-

in will be evaluated at this lower dose level following the same stopping rules. If acceptable toxicity is observed, the study will proceed to the randomized component. Patients who do not receive 14 days of Ibrutinib for reasons other than toxicity or DLT will be replaced for the purposes of the safety and tolerability assessment.

Randomized Phase 2

The main study is a randomized, double-blind placebo-controlled trial. The primary endpoint of the phase 2 component is the proportion of randomized patients with respiratory failure or death during hospitalization for COVID-19 infection within 30 days of registration. Respiratory failure is defined as any of the following: 1) endotracheal intubation and mechanical ventilation, 2) extracorporeal membrane oxygenation, 3) high-flow nasal cannula oxygen delivery (i.e., reinforced nasal cannula delivering heated, humidified oxygen with fraction of delivered oxygen ≥ 0.5 and flow rates of ≥ 30 l/min), noninvasive positive pressure ventilation, or 4) clinical diagnosis of respiratory failure without initiation of one of above measures only when clinical decision-making is driven solely by resource limitation or if patient has DNI (Do Not Resuscitate) status. Patients will be randomized to each treatment arm in a 1:1 ratio utilizing a permuted block schedule. Randomization will be stratified on age (<60 years vs ≥ 60 years) and presence of comorbidities (yes vs no) (comorbidities defined in Appendix C).

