Design and Sample Size: Based on a study in China, we assume that the event rate is 40% with standard care and that the event rate can be reduced to 15% when Ibrutinib is added to standard care for COVID-19. With 60 patients and using a standard group sequential design, there is 82.8% power to detect a reduction in the event rate under the alternative hypothesis and constraining the one-sided type I error to 20%. Power was calculated using a z-test for the difference in two proportions, pooled variance, and adjustment for small sample sizes with the Casagrande-Pike-Smith correction (EAST v6.5; Cytel, Inc). There will be an interim analysis when 50% of randomized patients have been followed for 30 days from registration. The study will be stopped early if at the interim analysis the observed event rate is higher in the ibrutinib arm (Arm A) than in the control arm (Arm B). We will plan to over-accrue by about 10% for a total accrual goal of 66 patients.

Although the actual reduction in the event rate could be larger than 25%, it could also be as low as 20% and still be quite meaningful. Furthermore, there is uncertainty in the event rate of the control arm. For these reasons, we have incorporated increased flexibility at the time of the interim analysis to potentially increase the sample size if conditional power indicates promising results, and will thus implement an adaptive group sequential design (Chen, DeMets, Lan; 2004).

At the interim analysis, there are 4 possible outcomes: 1) the futility criteria are met and the trial stops early; 2) the conditional power is unfavorable ($<50\%$), and enrollment continues to the planned sample size without an increase in sample size; 3) the conditional power is in a promising zone (defined as conditional power $\geq 50\%$ and $< 82.8\%$), and sample size may be re-estimated with the original sample size updated to boost the power to a target of 82.8%, subject to a maximum sample size of 120; or 4) the conditional power is favorable ($\geq 82.8\%$), and enrollment continues to the planned

sample size without an increase in sample size. When using this procedure, no adjustment to the final test statistic or critical value from the original design is required to control the Type I error rate. In addition, if the conditional power is in the promising zone, we can choose not to increase the sample size beyond what was originally planned or by a flexible amount without penalty.

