Primary Endpoint Analysis: All randomized patients will be included in the primary endpoint analysis and analyzed in the treatment arm to which they were randomized (ITT population). The data will be analyzed using a one-sided Fisher's exact test and a promising signal declared if $p \leq 0.20$ and the event rate is lower in the experimental arm. Since the primary endpoint is to be measured within the first 30 days of registration, we do not expect that primary endpoint information will be missing. However, if there is data missing, the patient will be considered a treatment failure.

Sensitivity analyses include comparison between treatment arm when adjusting for stratification factors and other important variables such as type of cancer or more refined categories of standard of care therapy via logistic regression. If there are events for respiratory failure based on clinical diagnosis without an objective measure and driven solely by resource limitation or if patient has DNI (Do Not Resuscitate) status, a sensitivity analysis will compare arms excluding patients with these events. Sensitivity analyses will be performed for the ITT population and for eligible patients who receive their assigned therapy without a major protocol violation.

Adverse Event Stopping Rules: If there is no concerning safety signal in the lead-in cohort, and the study is able to continue to the randomized component as planned, we have included a plan for comparing toxicity at the interim analyses (first 30 patients across both arms). Accrual will be temporarily suspended to this study and discussion of the data with co-investigators and the data safety monitoring board will occur if we observe adverse events that satisfy the following criteria:

- If the percentage of grade 3/4 all-cause adverse events is at least 15% higher in the ibrutinib arm than in the standard of care arm. This would also include grade 2 hemorrhage if considered significant by the treating physician in collaboration with PI.
- If the percentage of grade 4 all-cause adverse events is at least 15% higher in the ibrutinib arm than in the standard of care arm
- If the percentage of grade 5 treatment-related adverse events is at least 5% higher in the ibrutinib arm than in the standard of care arm

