Appendix C: Institutional guidelines for management of COVID-19

Treatment Setting	Treatment Recommendations Regardless of Age, Comorbidities, or Immunocompromised Status
Outpatient Setting	Supportive Care
Inpatient Setting*	Mild Disease – Without pneumonia and requiring <4L of new O ₂ Supportive Care
	Moderate Disease – Pneumonia requiring hospitalization, not meeting criteria for severe disease OR no evidence of pneumonia, but requiring ≥4L of new O ₂ Consider Treatment**
	Severe Disease – Requiring mechanical ventilation OR impending respiratory failure requiring intubation (RR>30 breaths/min; O ₂ saturation ≤93% on room air; PaO ₂ /FiO ₂ ratio <300mmHg) Consider Treatment

*Treatment requires approval 24/7 – see [Appendix C](#)

**Strongly consider treatment if duration of illness ≥ 7 days

Table 1: Treatment Recommendations for Highly Suspected / Confirmed COVID-19

Setting / Severity of Illness	Description	Treatment
Outpatients	All outpatients	Supportive care
Inpatients Mild Disease	Inpatients without pneumonia and SpO ₂ > 94% on room air	
Inpatients Severe Disease	Inpatients with SpO ₂ ≤ 94% on room air; requiring supplemental oxygen, mechanical ventilation, or ECMO	Consider treatment and/or enrollment in clinical trial(s)
Treatment recommendations regardless of age, comorbidities, or immunocompromised status		

Table 2: Adjunctive Antimicrobial Therapies to Consider in Patient Meeting Criteria for Treatment

Medication	Dose	Indication for Use	Additional Information
Remdesivir	200 mg IV for 1 day Then 100 mg IV daily for 4 – 9 days (Refer to Table 5 in Appendix A) No adjustment for renal impairment/ ECMO	• Non-FDA-approved agent available via emergency use authorization	
 See Appendix A for additional information on how to obtain this product Baseline and daily serum creatinine and hepatic function labs required Avoid combination therapy with hydroxychloroquine/ chloroquine due to in vitro antagonism The clinical relevance of in vitro CYP drug-drug interactions has not been established.

Ibrutinib for COVID 19

Comorbidities: obesity, asthma, chronic heart, lung, kidney, or liver disease; poorly controlled diabetes mellitus; pregnancy; or active malignancy

Please refer to <https://osu.app.box.com/s/sgvwyweea5xx7mjoghfimcaekpq52hv> for most updated version of institutional COVID 19 guidelines

Table 2: Adjunctive Antimicrobial Therapies to Consider in Patient Meeting Criteria for Treatment			

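### Randomization is stratified but the primary Fisher test is not: a small, cheaply removed loss of size and power, with one stratification factor that is constant as written

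*Combined protocol and SAP*

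**What the plan says.** The Randomized Phase 2 text of Section 13 sets the allocation: "Patients will be randomized to each treatment arm in a 1:1 ratio utilizing a permuted block schedule". It continues "Randomization will be stratified on age", split at 60 years, and adds as a second factor "presence of comorbidities (yes vs no) (comorbidities defined in Appendix C" of the protocol. The synopsis repeats this.

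The Primary Endpoint Analysis paragraph of Section 13 sets the decision test: "The data will be analyzed using a one-sided Fisher's exact test". A promising signal needs p ≤ 0.20 and a lower event rate on ibrutinib. The strata appear one paragraph later: "Sensitivity analyses include comparison between treatment arm when adjusting for stratification factors", by logistic regression. That model has no part in the decision, and no reason is given for leaving the strata out of the primary test.

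On the factors themselves, Appendix C ends its list of comorbidities with "poorly controlled diabetes mellitus; pregnancy; or active malignancy". Inclusion criterion 2 in Section 5.1 requires "Active cancer, defined as a solid malignancy either undergoing active therapy, receiving therapy within 1 year", or a hematologic malignancy under therapy or observation.

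**The concern.** Blocking within strata of a prognostic factor removes that factor's between-arm variation from the treatment comparison. A pooled 2×2 test still charges for the variation, so it is somewhat conservative and gives back part of what the stratification bought. The plan itself regards age as prognostic: the synopsis and Section 4.1 both say the death rate rises with age.

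In a 60-patient signal-seeking trial run at one-sided 0.20, the main risk is missing a real effect, so avoidable conservatism in the decision test matters. The choice also has to be fixed before unblinding. If the pooled and adjusted results disagree, deciding afterwards which one counts would be data-driven.

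**Working it through.** **Inputs from the documents.** Section 13: control rate ("we assume that the event rate is 40% with standard care"), 15% on ibrutinib, 60 patients (30 per arm), one-sided 0.20, futility stop at half the patients if the ibrutinib rate is higher.

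**Inputs assumed, not in the documents.** Blocks of 4; 60% of patients aged 60 or over; age odds ratios from 1 to 6, equal in both arms. The strata simulations use N = 60 and omit the interim look and the sample-size re-estimation.

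**1. The plan's own power reproduces.** Inverting the Casagrande-Pike-Smith correction with n = 30 and d = 0.25 gives an effective n per arm of (nd − 1)²/(nd²) = (7.5 − 1)²/1.875 = 22.53. The pooled-null, unpooled-alternative z formula gives (0.25·√22.53 − 0.8416·√(2·0.275·0.725))/√(0.24 + 0.1275) = 0.655/0.606 = 1.081, which is 86.0% without an interim. Adding the futility look at information 0.5 gives 82.77%, against the stated 82.8%. The same method gives 78.67%, 67.99% and 64.66% for Scenarios 2–4, against 78.7%, 68.0% and 64.7%.

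**2. Exact behaviour of the planned Fisher test, 30 per arm, no strata.** Its size is 12.3% at a common rate of 40% (11.9% counting the futility stop) and at most 14.2% at any rate. Its power at 40% vs 15% is 87.6%, or 86.6% with the futility stop. The test is therefore already far below 20% before strata are considered.

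**3. Why ignoring the strata adds conservatism.** The pooled variance is p(1 − p) = 0.4·0.6 = 0.24. With blocking, only the within-stratum part is real.

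- Age odds ratio 3 (risks 25% and 50%): 0.4·0.25·0.75 + 0.6·0.5·0.5 = 0.225. The standard error is overstated by √(0.24/0.225) = 1.033. A z cut-off of 0.8416 acts like 0.869, so a nominal 20% becomes about 19.2%.
- Age odds ratio 6 (risks 17% and 55%): 0.4·0.17·0.83 + 0.6·0.55·0.45 = 0.205. The ratio is 1.082, the cut-off acts like 0.911, and 20% becomes about 18.1%.

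The expected effect is about 1 to 2 points of size.

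**4. Simulated size, 40% in both arms** (15,000 stratified trials per setting; Monte Carlo standard error about √(0.13·0.87/15,000) = 0.3 points):

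| Test | OR 1 | OR 3 | OR 6 |
|---|---|---|---|
| Pooled Fisher (planned) | 12.6% | 11.8% | 10.7% |
| Stratified exact | 12.8% | 13.0% | 13.1% |
| Pooled mid-P | 18.9% | 17.7% | 16.4% |
| Stratified mid-P | 18.8% | 18.6% | 18.8% |

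The stratified p-value comes from convolving the hypergeometric distributions of the strata. At odds ratio 3 the shortfall from 20% is 20 − 11.8 = 8.2 points. Stratifying recovers 13.0 − 11.8 = 1.2, and the other 7.0 are discreteness. At odds ratio 6 the shortfall is 9.3, of which 2.4 is due to the strata and 6.9 to discreteness.

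**5. Power from the strata alone** (pooled Fisher to stratified exact):

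- 40% vs 15%, a separate run of 20,000 trials: 86.6% to 86.2% at odds ratio 1, 87.5% to 87.5% at 3, 88.1% to 88.6% at 5.
- 50% vs 30%: 67.7% to 69.6% at odds ratio 3 (+1.9), 68.2% to 72.2% at 6 (+4.0).
- A further simulation gave changes of −0.8 to +0.1 points at odds ratio 1, +0.1 to +1.8 at 3 and +0.5 to +4.0 at 6.
- If both factors varied, with an odds ratio of 3 each (40% vs 15%): size 11.3% to 12.9%, power 87.6% to 88.4%.

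**6. Power from moving to stratified mid-P**, odds ratio 3: 87.3% to 92.1% (40 vs 15), 73.0% to 81.2% (40 vs 20), 67.7% to 77.7% (50 vs 30). Against pooled mid-P, stratifying adds only 0.5–1.1 points at odds ratio 3 and 0.8–2.8 at 6. Most of the gain is mid-P.

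**7. What mid-P gives up.** Exact enumeration puts the maximum size of pooled mid-P at 20.3% with 30 per arm and 20.5% with 33 per arm (the 66-patient accrual goal). A stratified mid-P example, with 12 and 18 per arm in two strata at 10% and 30% risk, gives 20.3%.

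**8. The comorbidity factor.** Active cancer is required for entry, and active malignancy counts as a comorbidity. Read literally, every patient is a yes, and the nominal four strata collapse to two age groups.

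**The case against.** The strongest reply is that nothing promised is broken. Section 13 states 20% as a constraint, Fisher's test honours it at every event rate, and the small-sample correction in the power calculation already anticipates such a test. An adjusted analysis is prespecified in the ITT population. Keeping a simple exact test primary in a 60-patient phase 2 is defensible when the like-for-like gain is about 0–2 points at a moderate age effect and slightly negative with none. All of that stands, and it makes this a modest point. It does not supply the missing reason for departing from the randomization. Nor does it answer the 20-point reductions in Scenarios 3 and 4, which the plan calls meaningful and where power is lower and the gain larger.

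A reader might infer that ignoring the strata is why the test falls so far short of 20%. The figures do not support that: with strata of no prognostic value, Fisher's size is already about 12.6%, and a stratified exact test stays near 13%. A reader might also credit stratification with the whole mid-P gain, but most of it comes from dropping Fisher's discreteness, which is a separate decision with its own cost. Finally, the change is not wholly free. The conditional-power zones and the operating-characteristics table were built on an unstratified statistic.

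**Conclusion.** The mismatch is real and small. Ignoring the strata costs about 1 point of size at an assumed age odds ratio of 3 and about 2.5 points at 6, on top of the larger shortfall that Fisher's discreteness causes anyway. The corresponding power cost is about 0–2 points and up to about 4 points. If age is not prognostic there is no cost, and stratifying could lose up to about 1 point.

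The documents do not support reading this as an inflated type I error or an overstated power. The error is in the safe direction, and exact Fisher power with the futility stop (86.6%) exceeds the stated 82.8%.

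These sizes rest on the assumed block size, age mix and odds ratios, and on simulations without the interim look or re-estimation. The constant comorbidity factor rests on none of these assumptions; it follows from the text alone.

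**What to change.** 1. Correct the stratum definition first. For stratification, take active malignancy out of the comorbidity list so that the factor can vary, or drop the factor and stratify on age only. Make Section 13, the synopsis and Appendix C agree.
2. Make the primary test a stratified exact test of Cochran-Mantel-Haenszel type over the randomization strata, one-sided 0.20, with the Mantel-Haenszel risk difference as the estimate. Use the factors as entered at randomization. Pool any stratum without patients in both arms, since its patients would otherwise contribute nothing to an ITT test. Keep the pooled Fisher test as a sensitivity analysis. This retains the 20% bound.
3. Optionally use the stratified mid-P version. It gains about 5–11 points over Fisher across the plan's scenarios, mostly from mid-P. State plainly that size is then no longer strictly guaranteed (pooled mid-P reaches about 20.5%).
4. Re-run the operating characteristics in Section 13, including the conditional-power zones, with the chosen test, and report its attained size. If the pooled Fisher test is kept, give the reason and its attained size.

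The cost is SAP wording and one re-run of the simulations, settled before unblinding. No extra patients or data are needed.

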Inclusion/Exclusion Criteria	
Inclusion Criteria
 
 1. Hospitalization for confirmed PCR positive COVID-19 infection 2. Active cancer, defined as a solid malignancy either undergoing active therapy, receiving therapy within 1 year, or a hematologic malignancy under active therapy or observation. 3. Age ≥ 18 4. Patients with evidence of pulmonary involvement who meet any of the followings; presence of infiltrates on chest X-ray or CT scan or need for supplemental oxygen $< 8\text{L}$ nasal cannula or pulse oximetry $< 94\%$ on room air. 5. Biochemical values within the following limits: 
 a. Creatinine clearance $\geq 25 \text{ ml/min}$ by Cockcroft-Gault equation b. Total bilirubin $\leq 1.5 \times$ upper limit of normal (ULN) unless bilirubin rise is due to Gilbert's syndrome or of non-hepatic origin c. Alanine aminotransferase (ALT) and aspartate aminotransferase (AST) $\leq 3 \times$ ULN 6. Hematology values must be within the following limits (no need to hold growth factors or blood products transfusion): 
 a. Absolute neutrophil count (ANC) $\geq 1000/\text{mm}^3$ independent of growth factor support b. Platelets $\geq 50,000/\text{mm}^3$ 7. Ability to swallow capsules or receive opened capsule content via nasogastric or enteral feeding tube as described in 7.2 8. Ability to provide informed consent indicating that they understand the purpose of and procedures required for the study, including biomarkers, and are willing to participate in the study. If a patient is unable to provide informed consent (e.g. does not possess decisional capacity), a legally authorized representative may provide consent for the patient. 9. Women of childbearing potential and men who are sexually active must be practicing a highly effective method of birth control during and after the study consistent with local regulations regarding the use of birth control methods for

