7.1.2 Randomized Double-Blind Phase 2 Study

In the phase 2 portion of the study, patients will be randomized in a 1:1 fashion to receive ibrutinib plus standard care for COVID-19 versus placebo plus standard treatment for COVID-19. The study is double blinded and each patient will be assigned a randomization number by the James blind pharmacy. The patient, treating physicians, study personnel, and outcome assessors will all remain blinded to group assignment until after the database is locked and blinded analysis is completed. Only the unblinded statistician and the pharmacy staff have access to the unblinded randomization list.

Patients may receive any additional therapies that are not prohibited in the section on concomitant medications. In this trial, cycles will be 7 days in length. Ibrutinib therapy will continue for 2 cycles (14 days). Dose of study drug should be held or modified for adverse events as outlined in **Section 7**.

Patients who develop respiratory failure but are determined by the principal investigator to have clinical benefit from treatment may continue on for the full course of treatment.

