We note that the above stopping rules may be adjusted at any time during the conduct of the trial and in consideration of newly acquired information regarding the adverse event profile of the treatment(s) under investigation. The study team may choose to suspend

accrual because of unexpected adverse event profiles that have not met the specified rules above.

Secondary Endpoints: At the final analysis, all adverse events will be summarized by grade, type, and attribution (regardless of attribution and treatment-related) for each arm. Time-to-event endpoints such as time to discharge and overall survival will be estimated for each arm using the method of Kaplan-Meier. Medians estimates and/or estimates at specific time points will be provided with 95% confidence intervals. The proportion of patients with viral clearance at the time of hospital discharge will be estimated with 95% confidence intervals for each arm. For all biomarkers, descriptive statistics (e.g., means, medians, standard deviations, interquartile range) and graphical displays will be used to characterize central tendency and variability over time. Values will be log transformed as appropriate to reflect biologic plausibility. We will evaluate for statistical trends over time among the biologic measurements, with multiple measurements per patient, using mixed effects models. Lastly, associations between baseline characteristics and the primary endpoint will be evaluated with logistic regression, adjusting for arm. These analyses will be largely descriptive, as a result of a limited sample size.

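### The comorbidity stratification factor counts the cancer that every eligible patient must have, so as written only age stratifies the randomization

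*Combined protocol and SAP*

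**What the plan says.** Section 13 (Randomized Phase 2) and the synopsis (Statistics/Sample Size Estimate) specify 1:1 randomization in permuted blocks with two stratification factors: age below 60 versus 60 or over, and "presence of comorbidities (yes vs no) (comorbidities defined in Appendix C").

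Appendix C, the institutional COVID-19 guideline, contains one such list: "Comorbidities: obesity, asthma, chronic heart, lung, kidney, or liver disease; poorly controlled diabetes mellitus; pregnancy; or active malignancy".

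Inclusion criterion 2 (Section 5.1 and synopsis) requires of every patient: "Active cancer, defined as a solid malignancy either undergoing active therapy, receiving therapy within 1 year", "or a hematologic malignancy under active therapy or observation".

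The primary analysis in Section 13 is a one-sided Fisher's "exact test and a promising signal declared if" p is at most 0.20 and the event rate is lower on ibrutinib. It does not use the strata. The sensitivity analyses include a logistic-regression "comparison between treatment arm when adjusting for stratification factors and other important variables".

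On implementation, Section 7.1.2 says: "Only the unblinded statistician and the pharmacy staff have access to the unblinded randomization list". The list and its coding are not in the documents.

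**The concern.** A yes/no stratification factor works only if both levels can occur. Here one listed condition is enough for a yes, one listed condition is active malignancy, and active cancer is an entry requirement. The no level is then empty.

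Two planned features would fail. The randomization would not balance the arms on non-cancer comorbidity, which the synopsis rationale and Section 4.1 both treat as prognostic (higher death rates with older age and with co-morbidities). The sensitivity model meant to adjust for the stratification factors would also contain a constant that cannot be estimated. The trial could then be reported as stratified on, and adjusted for, comorbidity when it was neither.

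**Working it through.** **1. Strata.** Nominal: 2 age levels × 2 comorbidity levels = 4. Under the written definition: 2 × 1 = 2. Excluding malignancy from the definition restores 4.

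**2. The plan's power figure does not depend on this.** Inputs from Section 13: 30 per arm, 40% versus 15%, one-sided 0.20, pooled z-test with the Casagrande-Pike-Smith correction, and a stop at half information if the event rate is higher on ibrutinib.
- The correction n = (n′/4)·[1 + √(1 + 4/(n′d))]², with n = 30 and d = 0.25, gives n′ = 22.53 per arm.
- Pooled-z power is 86.0% at n′ (91.7% without the correction).
- With the futility stop (bivariate normal, Z₁ > 0 and Z₂ > z₀.₈, correlation √0.5) it is 82.6%, against 82.8% stated.

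Strata enter neither this calculation nor the Fisher test.

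**3. Chance imbalance when comorbidity is left unstratified.** The documents give no prevalence π, so it is assumed and varied. With independent counts X_A and X_B, each Binomial(n, π), the quantity is P(|X_A − X_B|/n ≥ 0.20), enumerated exactly. The threshold is 6 patients at n = 30, 7 at n = 33 and 12 at n = 60 (the maximum of 120 after re-estimation).

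| Assumed π | 30 per arm | 33 per arm | 60 per arm |
|---|---|---|---|
| 30% or 70% | 12.0% | 8.0% | 2.2% |
| 50% | 15.5% | 10.9% | 3.5% |
| 85% | 4.6% | 2.5% | 0.3% |
| 30% under 60, 70% at 60 or over | 12.0% | 8.0% | 2.2% |
| 20% under 60, 80% at 60 or over | 7.5% | 4.5% | 0.9% |

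The last two rows assume age is split about evenly and balanced by the age strata. They show how far age stratification protects if comorbidity rises with age.

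**4. Effect on the primary test, averaged over all trials.** This is exact one-sided Fisher rejection at p ≤ 0.20, ignoring the interim. Assumed control event rates are 30% without and 50% with comorbidity; at π = 50% these average the plan's 40%. The alternative multiplies both by 0.15/0.40 = 0.375. At 33 per arm and π = 50%:
- Null rejection: 12.9% unstratified, 12.4% with equal comorbidity counts.
- Power: 88.8% against 89.0%.

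Over 30 or 33 per arm, π of 30-70%, and rates of 30%/50% or 25%/55%, the largest gaps within a setting are 1.2 points for null rejection (12.3% against 11.1%) and 0.7 points for power (87.6% against 88.3%). All average null rates lie between 11% and 13.3%, below the 20% design level.

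**5. Effect within imbalanced trials.** A gap of at least 20 points in a given direction occurs in 4.0-7.8% of trials (30 or 33 per arm, π 30-70%). Conditional on it:

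| Assumed control rates | Fewer comorbid patients on ibrutinib: null rejection; power | More comorbid patients on ibrutinib: null rejection; power |
|---|---|---|
| 30% / 50% | 21.0-23.4%; 90.5-95.2% | 5.7-6.2%; 76.1-85.6% |
| 25% / 55% | 26.3-29.9%; 92.0-97.2% | 3.3-3.9%; 68.0-84.1% |

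**The case against.** **The two terms may differ.** Appendix C does not define active malignancy, and a general guideline could mean something narrower than criterion 2, which admits a solid tumour treated within the past year and a hematologic malignancy under observation. The no level would then not be empty. This stands as a possibility, but the protocol calls all qualifying disease active cancer, so the literal reading is the natural one. The narrower reading would also leave a factor that mixes cancer activity with other comorbidity.

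**Staff may have scored only non-cancer conditions.** The list also names pregnancy, although criterion 10 makes pregnant women ineligible, so it was evidently not adapted to the trial. Appendix C also points to an external, updated guideline. Actual coding cannot be seen, so this is a defect in the written rule and not a demonstrated failure of the randomization.

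**The consequence is small.** This is correct for the average effect on the primary test. Permuted blocks in four strata would not guarantee exactly equal comorbidity counts either, so the gaps in step 4 are best-case gains. The conditional figures in step 5 rest on assumed prevalence and prognostic strength, and similar ones could be produced for any unstratified covariate. The difference is that the plan chose this covariate to balance.

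**Other analyses partly cover it.** Section 13 allows adjustment for other important variables and states that "associations between baseline characteristics and the primary endpoint will be evaluated with logistic regression, adjusting for arm". Section 2.2 lists baseline clinical features as exploratory. None of these names comorbidity. With about 18 expected events (33 × 0.40 + 33 × 0.15 = 18.15), the adjusted model can carry few covariates, which favours naming the important ones in advance.

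**Conclusion.** The point holds on the text: as written, the comorbidity factor is yes for every eligible patient, so age alone stratifies and the comorbidity term drops out of the adjusted model. The validity, size and stated power of the primary test are unaffected. The cost is interpretive: a planned safeguard against a prognostic imbalance is missing in a small trial, where a 20-point imbalance would arise in roughly 8-16% of trials at 30-33 per arm if prevalence is 30-70%. It would be rarer if prevalence is very high, if comorbidity tracks age closely, or if the sample size is increased. It should be fixed. The textual conclusion needs no assumption beyond reading active malignancy as covering the trial's own active cancer. The sizes rest on assumed prevalences and event rates.

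**What to change.** In Section 13 and the synopsis, define the factor as at least one Appendix C comorbidity other than malignancy, and use that same variable in the randomization list and in the adjusted sensitivity model.

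If randomization has begun, state how the stratum was actually coded, derive non-cancer comorbidity from the screening medical history (Section 12), and name it as a covariate in the adjusted sensitivity model.

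A yes/no composite balances overall comorbidity, not each condition separately.

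The cost is one phrase in two places and an updated list, or one coding statement and one named covariate. The primary test, sample size and visit schedule do not change.
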